## 9.8 FOLLOW-UP VISITS

Follow-up visits should be performed according to the schedule provided in Table 1. All attempts should be made to conduct each follow-up visit within the time interval specified in Table 1. Evaluations conducted outside the prescribed time period will be considered protocol deviations.

## 9.9 MANAGEMENT OF IOP AFTER SURGERY

This protocol recommends that no IOP-lowering medications should be administered to subjects after the surgery (0 meds on postop day 1) unless medically warranted. Investigators should use their clinical judgement and best practices in determining when and why IOP-lowering medications should be reintroduced and if a subject requires surgical re-intervention to manage IOP.

In the event of a steroid response (IOP increase), the Investigator should use his/her standard of care to treat an increase in IOP; however, hypotensive medications should be discontinued once the topical steroid has been discontinued within the reasonable timeframe as deemed appropriate by the investigator.

If a pressure rise is observed, a paracentesis may be performed as necessary. If a paracentesis is performed and there is no protocol-defined adverse event, the paracentesis will be documented in the subject's medical record, the applicable visit CRF and the Ocular Procedures log. If, however, the paracentesis is performed in conjunction with an AE, then the AE is recorded as such, and the paracentesis is also recorded on the AE CRF as a treatment for the protocol-defined AE (as well as the other CRFs mentioned above).

Medications which have been re-started by the investigator may be discontinued if the investigator's judgment is that the target intraocular pressure has been reached and the continued use of some or all of the therapy may not be required. Discontinuation of medications after re-introduction is recommended to be in the reverse order of re-

introduction. The rationale for discontinuation should also be documented in the study record by the investigator.

A record of all ocular hypotensive medications added, discontinued or changed will be documented on the appropriate Case Report Form for each scheduled visit or on a Case Report Form for an Unscheduled Visit, if necessary.

Another potential reason for intervention is hypotony. Intervention should only be considered if the hypotony has caused or is likely to cause sequelae such as a flat chamber or retinal detachment. No intervention is indicated when the vision is unchanged from screening, there is no persistent choroidal detachment, the anterior chamber is not flat with lens corneal touch, or the patient is asymptomatic. No intervention should be undertaken for hypotony which is not causing, or threatening to cause, a reduction in vision.

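### Section 9.9 gives conflicting guidance on hypotony: an 'or' list, read literally, rules out intervention in eyes that the sentences around it leave open to it

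*Combined protocol and SAP*

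**What the plan says.** The closing paragraph of section 9.9 (Management of IOP After Surgery) opens with "Another potential reason for intervention is hypotony". Three operative sentences follow.

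- First: "Intervention should only be considered if the hypotony has caused or is likely to cause sequelae such as a flat chamber or retinal detachment".
- Middle: "No intervention is indicated when the vision is unchanged from screening, there is no persistent choroidal detachment", and the list then ends with "the anterior chamber is not flat with lens corneal touch, or the patient is asymptomatic".
- Last: "No intervention should be undertaken for hypotony which is not causing, or threatening to cause, a reduction in vision".

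No other readable part of the document says how the four signs in the middle sentence combine.

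**The concern.** The middle sentence is a list of reassuring findings under a negative, closed with 'or'. Taken as written, each finding alone is sufficient for no intervention to be indicated. That reaches eyes with the very sequela, a flat chamber, that the preceding sentence gives as a ground for considering intervention. It also reaches eyes whose vision is threatened but not yet reduced, which the following sentence takes care not to exclude.

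What is at stake is patient management. This is an instruction to sites on when to act, and section 6.2 allows up to 10 of them. Sites that read the list differently could handle the same eye differently, each with the protocol text in support.

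**Working it through.** No sample size, power or error rate is involved, and the plan gives no figure to reproduce. The check is to set the three sentences side by side.

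**Form of each sentence.** The first and last are restrictions. The first permits consideration of intervention only where sequelae exist or are likely. The last excludes hypotony that neither causes nor threatens a reduction in vision. Neither requires intervention, and the two can be held together. The middle sentence is also a restriction, but its reach depends on whether one sign suffices or all four are needed.

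**Worked cases.** 'Open' means that the sentence does not rule out intervention. 'Out' means that it does.

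| Eye with hypotony | First sentence | Middle, any one sign | Middle, all four signs | Last sentence |
|---|---|---|---|---|
| A. Flat chamber with lens-corneal touch; vision unchanged but threatened | Open | Out (vision unchanged) | Open | Open |
| B. Flat chamber with touch; vision reduced by the hypotony; no persistent choroidal detachment | Open | Out (no choroidal detachment) | Open | Open |
| C. Sequelae likely but not yet present; vision threatened; all four signs benign | Open | Out | Out | Open |
| D. Chamber flat without touch; vision unchanged but threatened; other signs benign | Open | Out | Out | Open |

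**What the literal reading does.** Under 'any one sign', an eye escapes the middle sentence only if vision has changed, a choroidal detachment persists, the chamber is flat with touch and the patient has symptoms, all at once. By then a sequela has already occurred, so *likely to cause* in the first sentence has almost nothing left to act on. An eye whose vision is threatened but still unchanged is always caught by the first sign in the list, so *threatening to cause* in the last sentence is left almost without effect too.

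**Whether reading the list jointly cures it.** It removes the conflict in cases A and B but not in C and D. In C, a sequela that is only likely is open under the first sentence and ruled out by the middle one. In D, the chamber terms differ: the first sentence speaks of a flat chamber, the middle one of a chamber flat with lens-corneal touch. A flat chamber without touch is therefore a named sequela in one sentence and a benign sign in the next. Changing 'or' to 'and' would not by itself reconcile the paragraph.

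**The case against.** The strongest reply is logical. The first and last sentences only limit intervention, so a site that withholds it complies with all three. This stands. A reader might infer that sites cannot follow the three sentences in the same eye, and the text does not support that. What remains is that compliance on those terms empties two of the sentences' own provisions.

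A second reply is that the purpose is evident: leave benign hypotony alone, and consider acting where sequelae are present or likely. On that view the 'or' is loose drafting and the last sentence is a summary. This is plausible, but the text does not state the joint reading, and cases C and D persist under it.

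A third reply is that other text protects patients. Section 9.9 relies on clinical judgement for restarting medication and for surgical re-intervention to manage IOP, section 4.3 requires investigators experienced with the device, and section 14 provides for emergency deviations that protect a subject's well-being. These soften the practical effect, so it would be too strong to say that treatment is barred in practice. They do not cure the wording: the judgement clause does not name hypotony, and the hypotony paragraph is written as prohibitions.

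It is also tempting to measure the problem by counting. Four yes/no signs give 2^4 = 16 combinations, and 'any one benign' covers 16 − 1 = 15 of them, against 1 for 'all four benign'. That count only restates the difference between *any* and *all*. It treats every combination as equally likely, the documents give no frequencies for the combinations, and it says nothing about how many eyes would be affected.

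**Conclusion.** The point holds as one of conflicting guidance. Read literally, the middle sentence rules out intervention in eyes that the sentences on either side leave open, and the chamber terms do not match. It deserves correction because it is an operative patient-management instruction that could misdirect a site following it as written.

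Its size is one paragraph of protocol text. How many eyes it would touch cannot be estimated from the readable documents. The conclusion rests on the literal reading of 'or' and on no redacted passage settling how the signs combine.

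Two further inferences are not supported:

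- **Distorted safety results.** Ocular adverse events are recorded when they occur (section 10), hypotony is classed as early or late by its timing (footnote to section 10.2), and the summaries count eyes and reports by event type (section 11.5.1). None of these depends on whether the hypotony was treated. One criterion for a serious event in section 10.1 refers to the need for intervention, so some effect on seriousness grading is conceivable, but none is shown.
- **An effect on the primary endpoint.** The treatment-failure rule in section 9.9 concerns secondary IOP-lowering interventions, not interventions for hypotony. No effect on the primary endpoint, sample size, error rate or power is claimed.

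**What to change.** The sponsor's clinical lead should:

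1. reconcile the three sentences into one consistent set of conditions;
2. state whether any one or all of the listed signs are required for no intervention to be indicated;
3. make clear how likely sequelae and a threatened reduction in vision are to be treated when the listed signs are still benign;
4. use the same description of the chamber throughout.

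Which clinical rule is right is for the sponsor to decide, and none is proposed here. The cost is the rewording of one paragraph, with IRB review as section 14 requires for protocol modifications. No analysis, sample size or data collection changes.

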#### Secondary IOP-Lowering Interventions to Control IOP

If the subject requires another glaucoma procedure to control their IOP, the subject should continue to be followed according to standard of care until the adverse event resolves or 1 month post-re-intervention, whichever is longer. Following this, the subject should be withdrawn from the study.

Subjects who have a secondary IOP-lowering intervention will be considered treatment failures for the purpose of the endpoint analyses. These subjects will be included in the Safety Endpoint analyses through their withdrawal from the study.

### **9.10 WITHDRAWAL AND DISCONTINUATION**

All subjects have the right to withdraw at any point during the study without prejudice. The investigator can discontinue any subject at any time at his/her discretion, or if continued participation in the study would result in harm to the subject. All efforts should be made by the investigator to retain the subject in the study. If a subject withdraws prematurely from the study, a genuine effort must be made to determine the reason(s) the subject discontinued the study. The reason must be recorded in the subject's file and on the Study Exit Form.

### **9.11 SUBJECTS LOST TO FOLLOW-UP**

Subjects who do not show up for a follow-up must be contacted to attempt to have them come for the follow-up. For those subjects who cannot be reached every attempt should be made and documented. If a subject misses two consecutive follow-up visits without any contact with the study staff, the subject will be considered lost-to-follow-up unless there is a further communication by the subject.

## 10 ADVERSE EVENTS (AEs)

Adverse Events are defined below. Adverse events that occur in the eye during the trial, whether they are considered to be device related or not, must be documented in the subject's records. Date of the event, its severity, treatment (if any) and the assessed relationship of the event to the study device will be recorded on the Adverse Event Form. Conditions which exist at the time the subject is enrolled do not need to be recorded as adverse events unless they increase in severity during the study. Sites should document any known existing medical and ophthalmic conditions at the time of screening.

### 10.1 DEFINITIONS OF AE, SAE, SADE, USADE

Adverse Event	Any untoward medical occurrence in a subject who has been treated with the device that does not necessarily have causal relationship with the treatment.
Adverse Device Effect	Any unfavorable and unintended sign (including an abnormal laboratory finding), symptom, or disease that is possibly related to the study device.
Serious Adverse Event (SAE)	Any untoward medical occurrence that: 
 
• Results in death
 
• Is life-threatening
 
• Requires in-patient hospitalization or prolongs existing hospitalization
 
• Necessitates medical or surgical intervention to preclude permanent impairment of a body function or permanent damage to a body structure
 
• Sight threatening
 

Unanticipated Adverse Device Effect	Any serious adverse effect on health or safety, any life-threatening problem or death caused by, or associated with a device if that effect, problem, or death was not previously identified in nature, severity, or degree of incidence in the clinical investigational plan; or any other serious problem associated with a device that relates to the rights, safety, or welfare of subjects (21 CFR 812.3(s)). Any sight-threatening event, whether listed in the protocol or not, is considered to be reportable as a USADE

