## **9.3 INFORMED CONSENT AND POINT OF ENROLLMENT**

The IRB-approved informed consent will be presented and explained to each prospective subject by the investigator or a trained clinical professional. Once the subject has had ample time to read the consent form, has been informed of all aspects of the study, and has had an opportunity to ask questions, the subject will be given a choice to voluntarily confirm his or her participation in the study as documented by completion of the Informed Consent. After signing the Informed Consent and the HIPAA (Health Insurance Portability and Accountability Act) authorization, the subject can then proceed with the screening visit. The subject has the right to withdraw from the study at any time without consequences, as indicated in the Informed Consent Document.

The subject's signed and dated informed consent must be obtained before conducting any study specific procedures that are not part of the standard of care. Subjects are enrolled upon signing the ICD even if they subsequently fail to meet the eligibility criteria.

The principal investigator(s) must retain the original, signed written Informed Consent Document. A copy of the written Informed Consent Document must be given to the subject.

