## 10.2 LIST OF ANTICIPATED POTENTIAL ADVERSE EVENTS

Anticipated potential adverse events listed below include those that might reasonably be expected to occur in this study because they are associated with glaucoma, ab-interno transluminal viscoelastic delivery, trabeculotomy, and/or the risk analysis for OMNI System. Adverse events may occur intra-operatively or post-operatively.

- [REDACTED]

 To avoid double counting an event, events of IOP  $\geq$  10 mmHg above baseline IOP at  $\geq$ 1 month visit that require management with systemic medication or secondary surgical intervention should be reported as “IOP increase requiring management with systemic medication at  $\geq$ 1 month visit” or “Need for secondary surgery intervention to manage IOP,” respectively.

 Hypotony is defined as “early” if it occurs within 2 weeks of surgery and “late” if it occurs more than 2 weeks after surgery

---

•

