### 10.3 REPORTING ADVERSE EVENTS AND UNANTICIPATED ADVERSE DEVICE EFFECTS

Identification, collection and reporting of adverse event information is the responsibility of the principal investigator. The investigator records the date of the event, its severity, treatment (if any) and the assessed relationship of the event to the study device on the Adverse Event Case Report Form (AE CRF).

Any ocular-related **serious adverse event (SAE)** should be reported to the study sponsor within one business day of learning of the event. Non-ocular-related SAEs should be reported to the study sponsor within two working days of learning of the event. Email the AE CRF to [[contact]](mailto:[contact]).

Any **unanticipated adverse device effects (UADE)** must be reported to the following two entities:

1. The study sponsor – Within one working day of the investigator first learning of the event, e-mail the AE CRF to [[contact]](mailto:[contact]); and
2. The reviewing IRB – As soon as possible, but no later than 10 working days after the investigator first learns of the event, report per the IRB's instructions.

The sponsor will conduct an evaluation of unanticipated adverse device effects. If the sponsor determines that an unanticipated adverse device effect presents an unreasonable risk to subjects, parts of the investigation presenting risks will be terminated. Termination will occur no later than 5 working days after the sponsor

makes such a determination and no later than 15 working days after the sponsor first received notice of the effect.

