### **11.5.1 ADVERSE EVENT**

Adverse events (AEs) will be classified as pretreatment, intraoperative or postoperative. The number and the percent of eyes reporting at least 1 adverse event of a given type will be summarized. Additionally, the number of reports of each type of AEs will be provided.

For each AE, the number and the percent of eyes reported with the event will be summarized by the severity level. For eyes with multiple reports of the same type of AE, the maximum severity will be used. Similarly, the AE relationship to the procedure will be summarized. For eyes with multiple reports of the same type of AE, the closest relationship to the procedure will be used.

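### The AE definition is limited to treated subjects although a pretreatment AE class is planned, and washout events in subjects never treated enter no planned safety table

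*Combined protocol and SAP*

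**What the plan says.** All references are to the combined protocol and SAP.

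- **Definition.** Section 10 opens with "Adverse Events are defined below", and Section 10.1 then gives "Any untoward medical occurrence in a subject who has been treated with the device", with no requirement of causality.
- **Timing.** Section 10.2 says "Adverse events may occur intra-operatively or post-operatively". Section 11.5.1 says "Adverse events (AEs) will be classified as pretreatment, intraoperative or postoperative".
- **Reference point.** Section 10 says "Conditions which exist at the time the subject is enrolled do not need to be recorded as adverse events" unless they worsen during the study. It also requires adverse events in the eye during the trial to be documented whether or not they relate to the device.
- **Enrollment and washout.** Section 9.3 says "Subjects are enrolled upon signing the ICD even if they subsequently fail to meet the eligibility criteria". Under Section 9.5, subjects on hypotensive medication stop it after screening, and eligibility is finally decided at the Baseline visit.
- **Serious events.** The SAE definition in Section 10.1 begins "Any untoward medical occurrence that" and does not mention treatment with the device. Under Section 10.3 an ocular SAE "should be reported to the study sponsor within one business day of learning of the event"; a non-ocular SAE is to be reported within two working days.
- **Analysis set.** Section 11.5 puts every safety analysis on the ITT set, and Section 11.2 defines ITT as subjects both enrolled and treated.

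**The concern.** The preoperative washout is a protocol step that carries risk, and exclusion criterion 4 in Section 8.2 recognises this. It takes place after enrollment and before treatment. A subject can consent, stop medication, have an adverse event, and then leave without surgery, either as ineligible at Baseline or by withdrawal under Section 9.10.

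Two things are at stake. First, the definition and the planned pretreatment class do not agree on whether an event before surgery is an adverse event at all, so a site reading Sections 10 to 10.2 gets mixed signals for a non-serious one. Second, the loss from the safety tables is selective. A pretreatment event mild enough to let surgery go ahead can be counted, while one that stops the subject from being treated cannot.

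**Working it through.** The plan gives no figure on this point, so the check is a comparison of passages.

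**Step 1: two readings of the definition.** The limit to treated subjects can be taken in two ways.

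| Reading of 10.1 | What the pretreatment class in 11.5.1 can hold | Subject washed out, never treated |
|---|---|---|
| It limits when an event counts (after treatment) | Nothing; 10.1 and 11.5.1 conflict | Not counted |
| It limits which subjects count (those treated at some point) | Pre-surgery events of subjects treated later | Not counted |

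The second reading lets 10.1, 11.2, 11.5 and 11.5.1 stand together. The last column is the same under both.

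**Step 2: the analysis set alone gives the same result.** Enrollment is at consent (9.3), washout follows screening, and final eligibility comes at Baseline (9.5). The status of enrolled, washed out and untreated is therefore possible. ITT requires treatment (11.2) and all safety analyses use ITT (11.5). Because Section 11.5 says all, its redacted subsections are stated to use the same population.

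**Step 3: collection.** Three items point to collection from enrollment: ocular events during the trial must be documented (10), only conditions already present at enrollment are exempt (10), and AE assessment is on the list of study procedures (Appendix A, 20.1). The pointer in Section 10 to the treated-only definition in 10.1 points the other way. The visit schedule (Table 1), the Baseline visit section (9.6) and part of 9.5 cannot be seen and may settle it. Serious events are clearer, because neither the SAE definition nor the reporting rule in 10.3 is limited to treated subjects.

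**Step 4: other records.** Section 9.10 puts the reason for withdrawal in the subject's file and on the Study Exit Form. That is a reason for leaving, without the severity, treatment and relationship that Section 10 asks for on the AE form. Individual data listings are optional (11.4).

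**Step 5: size.** Let *T* be the number treated, *t* the treated subjects with a pretreatment event, *k* the untreated subjects with one, and *u* the untreated subjects without one. The planned table can show at most *t/T*. On all enrolled subjects the proportion is (*t* + *k*)/(*T* + *k* + *u*), which exceeds *t/T* only if *k*/(*k* + *u*) > *t/T*. The documents give none of *t*, *k* or *u*, and the planned enrolled and treated numbers are redacted. Neither the size nor the direction of the change in the percentage can be stated. What is certain is that the *k* subjects are not counted.

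**The case against.** The strongest case for the plan is that this is a single-arm post-market study of a cleared device, so device safety belongs on treated subjects. Sections 11.2, 11.3 and 13.3 use that scope consistently. On the second reading of 10.1 the sections fit together, and the sentence in 10.2 is permissive and introduces a list of anticipated events, so it need not limit collection. Serious and sight-threatening washout events reach the sponsor in any case, exclusion criterion 4 removes subjects judged at significant washout risk, and only subjects on medication are washed out.

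Much of this stands, and it is why the point is minor. It does not close the tabulation gap. Reporting an SAE to the sponsor does not place it in a table, and the plan itself created a pretreatment class that leaves out the subjects whose events kept them from surgery.

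Three stronger readings are tempting but not supported:

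- A reader might infer that the pretreatment class must be empty. That needs the strictest reading of 10.1; the looser one is at least as natural.
- A reader might infer that non-serious washout events are not collected. The visible text leans the other way, and the unseen schedule may resolve it.
- A reader might infer that the reported pretreatment AE rate will be too low by some amount. Without counts, and with uneventful untreated subjects also entering an all-enrolled denominator, the percentage could move either way.

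**Conclusion.** The point holds in a limited form. Sections 10, 10.1, 10.2 and 11.5.1 do not agree on whether events before surgery are adverse events and must be reconciled. On either reading of 10.1, an adverse event during the preoperative washout in a subject who is then not treated enters no planned safety table. Collection of non-serious events in such subjects is unsettled rather than absent.

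The severity is minor. The safety analysis is descriptive, and no hypothesis test, sample size or effectiveness result is affected. The number of subjects concerned cannot be estimated. The conclusion on tabulation rests on the stated ITT definition being applied as written. The conclusion on collection rests on visible text only and could change with the redacted part of 9.5, Section 9.6 or Table 1. Events during the 12-month washout are outside this point, since those subjects have been treated.

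**What to change.** 1. State in Section 10.1 that AE collection starts at consent (or at the start of washout), and bring Sections 10, 10.1, 10.2 and 11.5.1 into line with that.
2. Add to Section 11.5 one descriptive table or listing of pretreatment adverse events for all enrolled subjects, as a stated exception to the ITT rule. Give a separate line for subjects who began washout and were not treated, with the number who began washout as its denominator.
3. Count a re-screened person once, because Section 9.4 assigns a new identification number at the second screening.
4. Keep intraoperative and postoperative adverse events on the treated set.

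The cost is one more descriptive table or listing, and AE forms for some subjects who are never treated. No visit, test, sample size or clinical rule changes. If the unseen parts of 9.5, 9.6 or Table 1 already fix the start of collection, the first item reduces to aligning the wording; the second is still needed.
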